6.2 Exclusion criteria

Participants are not permitted to enrol in the study if one or more of the following criteria are met:

1. Participants who have limited or no understanding of spoken and/or written English.
2. Other diagnosis of cancer, not including basal cell carcinoma of the skin or cervical carcinoma in situ, within the previous 5 years.

Participants are not permitted to take part in Stage 2 if one or more of the following criteria are met:

1. Co-morbidities incompatible with study participation e.g. that result in a participant being unable to complete daily entries satisfactorily via his/her smartphone.

2. Known and/or treated Sleep apnoea.
3. Regular shift work or night work (defined as >1 overnight shift per month)
4. Breast feeding.

6.3 Concomitant Medication

Concomitant Sleep Medication:

Participants are permitted to continue taking existing sleep medication (usage to be documented). Introduction of new sleep medication during the three-week study period is not permitted.

7 TRIAL PROCEDURES

Table 1. Assessment Schedule

Assessment/ Procedure	Stage 1		Stage 2		
	Screening (-14 days)	Day 0	Screening (-28 days) ⁵	Day 0	Days 1-21
Stage 1:					
Informed Consent ¹ for Stage 1 & Registration	x				
ISI ²		x			
EQ-5D-5L ²		x			
FACT-ES ²		x			
Demographics ²		x			
Sleep History ²		x			
Stage 2:					
Informed Consent for Stage 2 ¹			x		
Review Eligibility Criteria			x		
Cancer Medical History				x	
Current Cancer Treatment				x	
Current Co-Morbidities				x	
Digital Diary Download ³				x	
Daily Sleep Diary Entry ³					x
ISI ²					x
EQ-5D-5L ²					x
FACT-ES ²					x
UEQ ²					x
Adverse Events ⁴					x

¹ Where possible will be online remote eConsent but can be completed in clinic (online/paper).

² Participant completes online questionnaire (paper questionnaires will be available for clinic use).

³ Participants completes on their own smartphone.

⁴ AEs will be collected at follow-up telephone consultation at Day 21 (+8 days).

⁵ Stage 2 Consent should occur no later than 28 days post Stage 1 Consent, however ideally this would occur as soon as possible after consent for Stage 1 has been provided.

7.1 Recruitment

Recruitment will take place at the Christie NHS Foundation Trust over a four-month period and is planned to end (last participant enrolled) by January 2022.

7.2 Participant identification

Stage 1 of the study will involve members of the clinical team identifying potential participants from the breast cancer clinic database at the Christie Hospital. Patient records will be used to assess inclusion and exclusion criteria to identify participants who are potentially eligible for the first stage of the study. These potentially eligible breast cancer participants will be invited to take part in the study. Recruitment will be complete when we reach the target sample size of 285 participants.

7.3 Stage 1

Participants will be recruited to Stage 1 of the study remotely and if required, in-person through attendance at the breast cancer clinic at the Christie NHS Foundation Trust.

7.3.1 Stage 1 Electronic Consent (eConsent)

Participants will be contacted by the clinical study team by text message. This text message will give some brief information about the study and an internet link to the study information including the Patient Information Sheet (PIS) and Informed Consent Form (ICF). If required, initial contact can also occur by email, telephone and/or online video conferencing. In these instances, the potentially eligible participant will be provided with the same internet link as above. Moreover, the initial contact can also be face to face in the clinic. The PIS and ICF to be used in the study will be approved by the Research Ethics Committee (REC) and follow GCP guidelines. These documents have been designed to be viewed and completed by patients on their smartphone. If required, these documents can also be accessed by a computer or tablet. Patients will be given time to consider taking part in the study and provided with contact details of the clinical study team to discuss any questions they may have regarding the study. If willing to participate, they will be asked to complete the ICF. At this stage the participant will be asked to provide their email address and mobile phone number for the purposes of sending study questionnaires and further study information. If no response has been received from potential participants within 3 days of the receiving the first text message, the initial text message will be sent again.

A proportionate approach to eConsent in guidance with the MHRA/HRA Joint Statement regarding seeking consent using electronic methods will be taken²². The HRA indicate that it is not necessary to include a PIS or ICF for online questionnaire-based research²³. However, we have taken the decision to provide patients with these documents to ensure they have sufficient information to enable them to reach an informed decision to take part. As the study is observational and low risk, participants will confirm participation in the trial by simple e-signature on the ICF. Within the ICF, participants will be asked to consent to the use of their personal data for the purposes of sending online questionnaires and for the Sponsor to have access to this data for monitoring purposes. Participants will also be asked to consent to being contacted to take part in Stage 2 of the study. See Figure 1 for an outline of the eConsent process.

[figure not shown]

Figure 1. Outline of eConsent process using Qualtrics^{XM} platform.

Qualtrics^{XM} will be used as the online platform for providing patients with the study information, PIS and ICF, remotely. This platform is General Data Protection Regulation (GDPR) compliant and is ISO 27001 certified ensuring Qualtrics^{XM} meets the international standard defining requirements for Information Security Management System (ISMS). The clinical study team will be provided with a secure Clinical Study Team Qualtrics^{XM} User Account. This user account will be given a username and password for access only by authorised individuals in the clinical study team.

Once a participant completes and submits their online ICF, the information is saved within the Clinical Study Team Qualtrics^{XM} User Account. The Qualtrics^{XM} platform will be directed to send a copy of the PIS and completed ICF to the participant via email. A copy of the ICF will also be forwarded via email to the study team for downloading and storage in the Investigator Site File (ISF) and patient medical record.

As mentioned, the eConsent process can be performed face-to-face in clinic. Participants can complete the consent process directly online on their smartphone. If this is unavailable, a tablet can be provided, or paper documentation can be supplied. If completed on paper, clinic study staff will need to enter relevant data into Qualtrics^{XM} platform to activate downstream processes for Stage 2 of the study.

7.3.2 Participant Registration

The clinical study team will be notified of consenting participants through the delivery of completed ICFs via email from the Qualtrics^{XM} platform. Upon receiving an ICF, they will review ICF to ensure completeness and register the patient into the eCRF. This will include entering the patient's mobile number and email address into the eCRF for remote questionnaire delivery. An anonymous participant identification number (PIN) will be assigned to the patient by the Electronic Data Capture (EDC) system. This PIN will also be used as a unique identifier within the Qualtrics^{XM} platform. See Figure 2 for an outline of Stage 1 study procedures.

[figure not shown]

Figure 2. Outline of Stage 1 study procedures including informed consent.

Upon submission of a completed ICF, the Qualtrics^{XM} platform will store the participant's contact details within the Qualtrics^{XM} Directory which is securely located within the Clinical Study Team Qualtrics^{XM} User Account. These contact details will be used for sending Stage 2 specific-study information to participants who are eligible for the second stage of the study.

7.3.3 Questionnaire Completion

Following completion of patient registration into the eCRF, the electronic Patient Reported Outcomes (ePRO) module of the eCRF will be activated to send a text message (or email, if required) containing a link to the baseline questionnaire set to consenting participants. This questionnaire set consists of five short questionnaires including:

- Insomnia Severity Index: ISI
- Quality of life: EQ-5D-5L and FACT-ES
- Demographics and sleep history: age, gender, weight, height, ethnicity, marital status, educational level, current occupation, pregnancy, breastfeeding, menopausal status, shift-work/night-work and smartphone access. Sleep-related questions to determine if the patient has experienced sleep disturbance prior to the screening/baseline consultation with beginning or worsening of sleep disturbance since breast cancer diagnosis and if patient has suffered or currently suffering from sleep apnoea.

The participant can complete the questionnaires on their smartphone. It is estimated the participant will take 20-25 minutes to complete these questionnaires. If the participant does not complete the baseline questionnaire within 3 days, the eCRF will send a questionnaire reminder text message (or email, if required). This will be repeated on two subsequent occasions if the questionnaire remains uncompleted for the three preceding days. The eCRF can be configured to notify the clinical study team by email when a participant completes the questionnaire set. Questionnaires can also be completed on computer or tablet however smartphone completion is preferred.

The baseline questionnaire set can be completed on paper if the clinic, however clinic study staff will be required to subsequently enter the data recorded by the participant directly into eCRF.

7.4 Stage 2

Briefly, Stage 2 will run separately from Stage 1 to aid the timely recruitment and flow of participants through the study. Participants will be asked to consent to taking part in Stage 2, separately from the consent to take part in Stage 1. As participants in Stage 1 will have consented to the use of their contact details for the purposes of being invited to take part in Stage 2, all recruitment and procedures in Stage 2 will be carried out remotely. Figure 3 describes Stage 2 procedures.

[figure not shown]

Figure 3. Outline of Stage 2 study procedures.

7.4.1 Stage 2 Eligibility Assessment

All questionnaire-derived eligibility-related data for each participant will be present within the eCRF. This will enable the clinical study team to populate the eligibility eCRF including ISI scores and data related to self-reported sleep history, sleep apnoea, shift-work or night-work, possession of smartphone and breast feeding. The EDC will be configured to automatically calculate the total ISI score required for assessment of eligibility to Stage 2. The clinical research team will be required to confirm from patient medical records the stage of breast cancer, any other diagnosis of cancer, not including basal cell carcinoma of the skin or cervical carcinoma in situ, within the previous 5 years, and any comorbidities incompatible with study participation.

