10 STATISTICS AND DATA ANALYSIS

10.1 Sample size calculation

The sample size required for Stage 1 is based on an assumed prevalence of insomnia of 44% in breast cancer patients (midway point of insomnia prevalence range found in breast cancer patients 19-69%)⁴⁻¹⁰. A sample size of 267 participants is required for estimating the expected prevalence rate with 5% absolute precision and 90% confidence or 6% absolute precision and 95% confidence²⁹.

The target for Stage 2 is for approximately 100 participants to complete the study, to provide sufficient data to assess the secondary objectives. With an assumed prevalence of 44% and a 20% drop out rate, then 285 participants in Stage 1 would give an expected 125 eligible participants for Stage 2 with 100 participants assumed to complete the 3-week observation period.

Therefore, the study will aim to recruit a minimum of 285 patients into Stage 1 to cover the sample size requirements for Stage 1 and Stage 2.

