## Statistical Analysis Plan for CLM-INS-004

Version: Final 2.0

Date: 9th September 2022**DOCUMENT REVISION HISTORY**

VERSION	DATE	AUTHOR/ UPDATED BY	COMMENTS
2.0	9 th September 2022	[name]	Amended definition of analysis sets to only include patient eligible for the study and added that baseline BMI would be reported

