### 2.2. Definitions of Analysis Sets

The following analysis sets will be used in the statistical analyses and reporting of study data.

- Stage 1 analysis set will include all participants who consented to stage 1, are eligible for the study and have evaluable data for at least one of the questionnaires (ISI, EQ-5D-5L or FACT-ES).
- Stage 2 analysis set will be a subset of the Stage 1 analysis set and will include eligible Stage 1 participants who scored  $\geq 8$  on their baseline ISI questionnaire and consented to stage 2. Note if a patient consents to Stage 2 but does not provide **any** stage 2 data (e.g., questionnaire/sleep data) then they will be excluded from the stage 2 analysis set.

Statistical Analysis Plan for CLM-INS-004

Version: Final 2.0

Date: 9th September 2022

Note, listings will generally be based on the stage 1 analysis set with an indicator for patients who also entered into stage 2, with the exception of the cancer history, cancer treatment, co-morbidities, sleep diary, AE and UEQ listings which will be based on the stage 2 analysis set since these are only completed for stage 2 patients.

If a participant does not enroll in the digital diary (i.e., does not even download the app) but completes the UEQ, then data from the UEQ will not be included in the reporting of the data.

Percentages will generally be derived based on the analysis set N as the denominator, unless stated otherwise. Where there is missing data, % may be derived based on those within the analysis set who have evaluable data. Where applicable missing categories will be included to show the number of patients with missing data for the relevant endpoint.

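### Stage 1 eligibility is re-checked from records only when ISI is 8 or more, yet SAP v2.0 removes ineligible patients from the primary denominator: a risk of downward bias of unknown size

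*Protocol*

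**What the plan says.** **First record screen, for everyone.** Under Protocol 7.2 the clinical team checks records against the inclusion and exclusion criteria before invitation, to "identify participants who are potentially eligible for the first stage of the study".

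**Second record check, on the Stage 2 path.** Protocol 7.4.1, on Stage 2 eligibility, says: "The clinical research team will be required to confirm from patient medical records the stage of breast cancer". The same sentence adds other cancer within 5 years and incompatible co-morbidities. Cancer stage and other cancer are Stage 1 criteria (Protocol 6.1 and 6.2); co-morbidities are a Stage 2 exclusion. Protocol 4 sends only participants scoring 8 or more on the ISI to Stage 2 assessment. Table 1 in both documents lists the eligibility review under Stage 2 alone.

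**Cancer data.** Time since diagnosis, stage and treatment are captured from records only after Stage 2 consent (Protocol 7.4.4). SAP 2.2 confirms that these forms exist only for Stage 2 patients.

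**Primary denominator.** SAP 2.2 defines the Stage 1 set as "all participants who consented to stage 1, are eligible for the study and have evaluable data for at least one of the questionnaires". SAP 3.2.1 takes the primary prevalence, with its exact 95% interval, on that set. The revision history for v2.0 records: "Amended definition of analysis sets to only include patient eligible for the study". The SAP does not say from what source, or when, the eligibility of a participant with ISI below 8 is established.

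**The concern.** Prevalence is the share of the Stage 1 set with an ISI of 8 or more. If two patients both fail a Stage 1 criterion but slipped through the first screen, the one scoring 8 or more meets a second record check and can be removed from numerator and denominator. The one scoring below 8 meets no planned second check and stays in the denominator as a non-case. The exclusion rule is the same for both, but the chance of being caught depends on the primary outcome.

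At stake is a one-directional error in the primary estimate that the Clopper-Pearson interval does not reflect. No planned output would show whether it had occurred: SAP 3.1.1 reports numbers consented and numbers in each set, but not exclusions split by ISI.

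**Working it through.** **Inputs from the documents.** Prevalence p = 44%; n = 267 "with 5% absolute precision and 90% confidence or 6% absolute precision and 95% confidence"; Stage 1 target 285, about 125 eligible for Stage 2, 100 completing, 20% dropout (Protocol 10.1).

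**The plan's own figures.** With n = z²p(1 − p)/d²:
- d = 0.05, 90% confidence: 266.7, so 267.
- d = 0.06, 95% confidence: 262.9, so 263, close to the stated 267.
- 285 × 0.44 = 125.4 and 125.4 × 0.8 = 100.3, which match 125 and 100.

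**Assumptions.** Let e be the share of enrolled patients who are ineligible despite the first screen, and q the prevalence of ISI of 8 or more among them. The documents give neither.

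**Only ineligible cases found and removed:**

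estimate = (1 − e)p / [(1 − e) + e(1 − q)]

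This lies below p for any e above 0 and q below 1. With q = p = 44% it becomes (1 − e)(0.44)/(1 − 0.44e):

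| e | Estimate | Shift (points) |
|---|---|---|
| 1% | 43.75% | −0.25 |
| 2% | 43.5% | −0.5 |
| 5% | 0.418/0.978 = 42.7% | −1.3 |
| 10% | 0.396/0.956 = 41.4% | −2.6 |
| 20% | 0.352/0.912 = 38.6% | −5.4 |

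Varying q from 30% to 60% gives −1.6 to −0.9 points at e = 5%, and −3.2 to −1.9 at e = 10%. A shift equal to the planned 6 points needs e = 0.06/(0.44 − 0.38 × 0.44) = 0.06/0.2728, about 22%.

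**Partial detection.** If a proportion D1 of ineligible cases and D0 of ineligible non-cases is found, with q = p:

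estimate = p(1 − e·D1) / {1 − e[p·D1 + (1 − p)D0]}

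With D1 = D0 this returns p, so there is no bias. With D1 = 1, D0 = 0.5 (an illustration) and e = 5%: 0.418/(1 − 0.05 × 0.72) = 0.418/0.964 = 43.4%, a shift of −0.6, about half the one-sided value.

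**In counts, from 125/285 = 43.9% (exact 95% CI 38.0 to 49.8), removing cases only:**
- 5 removed: 120/280 = 42.9% (−1.0)
- 10 removed: 115/275 = 41.8% (−2.0)
- 20 removed: 105/265 = 39.6% (−4.2)

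**Removing nobody.** The error is e(q − p). It is zero if q = p; at e = 5% it is 0.05 × (0.30 − 0.44) = −0.7 points for q = 30% and 0.05 × (0.60 − 0.44) = +0.8 for q = 60%.

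**The case against.** The strongest reply is that bias needs two things the documents do not establish: that ineligible patients pass the first screen, and that those with ISI below 8 are then missed. The first screen covers everyone and uses medical records, as the second does, so the second may find little. Other routes do not depend on ISI: source data verification (Protocol 11.4), investigator sign-off before lock (11.5), monitoring visits (12), and a deviation category for inclusion and exclusion criteria in SAP 3.1.2. The restriction to ISI of 8 or more comes from reading Protocol 4 with 7.4.1 and Table 1; 7.4.1 alone does not state it. The protocol's flow chart and Figure 2 could not be read for this check and might show a Stage 1 confirmation step.

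Most of this stands, and it limits the point to a risk. It does not remove it. The extent of source data verification is not stated, and no cancer-history form is completed for Stage 1-only participants, so nothing planned in the text makes detection equal.

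A reader might also infer from the v2.0 amendment that ineligible patients had in fact been enrolled. The documents do not support that. The revision history gives neither a reason nor a count, although Protocol 10.5 asks for the reason, and SAP 4 calls the analysis-set entry a clarification. Even if such patients existed, nothing shows what their ISI scores were.

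**Conclusion.** The point holds as a risk of downward bias from differential verification of eligibility. The direction follows from the design: a second check of Stage 1 criteria is planned only for ISI of 8 or more, and the primary denominator is limited to eligible patients. The size is unknown. The one-sided figures assume that every ineligible case and no ineligible non-case is found, so at q = p they are the outer end for a given e. At 1% to 2% ineligible the shift is 0.25 to 0.5 points, small beside the planned 6; at 10% it is 2.6.

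Two stronger readings should be avoided. One is that prevalence is biased downwards as a matter of fact: the shift is zero if the first screen was complete or detection is equal. The other is that the exclusion rule itself depends on ISI: SAP 2.2 applies eligibility to all Stage 1 participants, and only the chance of detection differs.

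A related gap is that SAP 2.2 does not say which criteria make a patient eligible for the study. If Stage 2 exclusions such as co-morbidities were read into it, more cases would be lost from the primary estimate. Nothing here changes the sample size calculation.

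**What to change.** In SAP 2.2:

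1. Define eligibility for the Stage 1 set as the Stage 1 criteria only.
2. Exclude from the primary prevalence analysis only on eligibility information obtained the same way for all Stage 1 participants whatever their ISI. That means the pre-invitation screen or, where the site can do it, the same record confirmation for everyone. Equal confirmation is the stronger option, because it keeps the target population and removes the asymmetry.
3. Tabulate exclusions, with the criterion failed, by ISI below 8 and ISI of 8 or more.
4. Report prevalence with and without patients found ineligible only at the Stage 2 check.

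The cost is SAP wording, one small table and one further estimate; record confirmation for everyone would add site work. The contestable part is that a few patients known to be ineligible may stay in one of the two estimates. Their effect there is e(q − p), which can go either way; the second estimate shows how much it matters. If exclusions turn out to be balanced or absent, the table settles the question.

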7.4.2 Stage 2 eConsent

Within 28 days of consenting to Stage 1 of the study and following confirmation of a participants' eligibility to Stage 2, a clinical study team member will activate the Qualtrics^{XM} platform to send a Stage 2-specific PIS and ICF to the eligible participant via text message (or email, if required). Again, the patient will be given time to consider taking part in the study and provided with contact details of the clinical study team to discuss any questions they may have regarding the study. Once a participant completes and submits their online Stage 2-specific ICF, the Qualtrics^{XM} platform will send a copy of the Stage 2 PIS and completed ICF to the participant via email and a copy of the ICF to the study team. If no response has been received from potential participants within 3 days of the receiving the Stage 2 invite text message, this text message will be sent again. This will be repeated once more, 3 days later if no response has been received.

7.4.3 Digital Sleep Diary

Upon receiving and reviewing completed Stage 2-specific ICF, the study team will assign a participant-specific digital sleep diary code to the participant provided by Closed Loop Medicine and enter this code into the eCRF. Within the eCRF the study team will confirm consent for Stage 2 has been obtained and then instruct the ePRO module of the eCRF to send the participant via text message (or email if required) instructions for downloading, enrolling, and using the digital sleep diary app on their smartphone. The participant will also be asked to complete a short questionnaire to confirm they have downloaded and enrolled into the app. This is required for the automation of delivery of End of Study Questionnaire Set by the eCRF at day 21. If the short questionnaire is not completed by the participant within 3 days, the eCRF will send a questionnaire reminder email or text message. This will be repeated again 3 days later if the download and enrolment procedure is not confirmed. If after 9 days the questionnaire still remains unanswered, a member of the research team will call the participant to determine if they are experiencing any issues with downloading the digital sleep diary app and provide assistance.

The participant will then complete the digital sleep diary each day for three weeks. Participants will be provided with contact information if they require assistance with downloading or using the app during the study period. This will be a study-specific email address to be received by members of the clinical study team. Participants requiring assistance will be contacted by a clinical study team member either by email or telephone. Where required, the clinical study team will access technical support directly from Closed Loop Medicine.

